6.5.1 Enfortumab Vedotin-Related Rash

Enfortumab vedotin is a Nectin-4 directed antibody drug conjugate. Nectin-4 is a cell adhesion molecule that is highly expressed in urothelial carcinoma. Low to moderate levels of Nectin-4 are also expressed on normal tissues, including skin keratinocytes, sweat glands and hair follicles; thus, skin reactions are anticipated events. As such, skin reactions are AEs of interest in all clinical studies with enfortumab vedotin.

A cumulative review of post-marketing safety data from 18 Dec 2019 (the approval date of enfortumab vedotin in the US) through 22 Oct 2020 identified reports of severe cutaneous adverse reactions in 15 subjects receiving enfortumab vedotin, some of whom had fatal outcomes. These reactions occurred predominantly during the first cycle of

treatment. AEs reported in these cases included Stevens-Johnson Syndrome (SJS) (5 cases), blister (3 cases), dermatitis bullous (3 cases), symmetrical drug-related intertriginous and flexural exanthema (SDRIFE; 2 cases), and 1 case each of dermatitis exfoliative, exfoliative rash, epidermal necrosis, oropharyngeal blistering, stomatitis and toxic epidermal necrolysis (TEN).

In enfortumab vedotin monotherapy studies of urothelial carcinoma, SAEs of severe cutaneous adverse reactions were reported in 11 of 749 subjects (1.5%) and included dermatitis bullous (0.4%), drug eruption (0.4%), blister (0.1%), conjunctivitis (0.1%), SJS (0.1%), stomatitis (0.1%) and toxic skin eruption (0.1%).

Subjects should be informed that rash and severe skin reactions have occurred after administration of EV, and to contact the Investigator immediately if they have signs and symptoms of skin reactions, oral mucosal and ocular abnormalities including mucositis or conjunctivitis. Starting in the first cycle and throughout treatment, closely monitor subjects for skin reactions. For mild to moderate skin reactions, consider appropriate treatment, such as topical corticosteroids and antihistamines as clinically indicated. For recommendations regarding dose modifications for skin reactions due to EV, refer to [\[Table 8\]](#).

6.5.2 Management of Hyperglycemia

Investigators should monitor blood glucose levels and are advised to perform additional assessments if any symptoms of hyperglycemia are observed, including a thorough evaluation for infection. In addition, if steroids are used to treat any other condition, blood glucose levels may require additional monitoring. If elevated blood glucose levels are observed, participants should be treated according to local standard of care and referral to endocrinology may be considered.

Participants, especially those with a history of or ongoing diabetes mellitus or hyperglycemia, should be advised to immediately notify their physicians if their glucose level becomes difficult to control or if they experience symptoms suggestive of hyperglycemia such as frequent urination, increased thirst, blurred vision, fatigue, and headache. Participants who enter the study with an elevated HbA1c ($\geq 6.5\%$) at baseline should be referred to an appropriate provider during Cycle 1 for glucose management. Blood glucose should be checked prior to each dosing and dose should be withheld for blood glucose > 250 mg/dL (13.9 mmol/L) (Grade 3 or higher). Dosing may continue once the participant's blood glucose has improved to \leq Grade 2 and participant is clinically and metabolically stable. Blood glucose > 500 mg/dL (27.8 mmol/L) (Grade 4) considered related to enfortumab vedotin requires treatment discontinuation. If a participant experiences new onset of diabetes mellitus, evaluate participants with a metabolic panel, urine ketones, HbA1c, and C-peptide to assess for new onset diabetes.

6.5.3 Management of Enfortumab Vedotin Infusion Related Reactions

An IRR may occur during the infusion of study treatment. The infusion should be administered at a site properly equipped and staffed to manage anaphylaxis should it occur. All supportive measures consistent with optimal participant care should be given throughout the study according to institutional standards. Supportive measures may include administering medications for IRRs.

Participants who experience an IRR may be premedicated for subsequent infusions. Premedication may include pain medication (e.g., acetaminophen or equivalent), an antihistamine (e.g., diphenhydramine hydrochloride), and a corticosteroid administered approximately 30 to 60 minutes prior to each infusion or according to institutional standards. Should a participant experience IRRs in the setting of premedication, continued treatment with enfortumab vedotin must be discussed with the medical monitor prior to the next planned dose.

If anaphylaxis occurs, study treatment administration should be immediately and permanently discontinued.

6.6 Continued Access to Investigational Product After the End of the Study

Options to provide enfortumab vedotin to participants who are continuing to receive treatment and are benefiting will be determined at the time of study closure.

6.7 Treatment of Overdose

Neither the effects of overdose of enfortumab vedotin nor an antidote to overdose are known. In the case of an overdose, the participant should be closely monitored for adverse reactions and supportive treatment should be administered.

Weight-based dosing for enfortumab vedotin is based on the participant's actual body weight, with the exception of participants weighing greater than 100 kg; doses will be based on 100 kg for these individuals. The maximum dose calculated per cycle in this study is 125 mg.

In the event of an overdose of enfortumab vedotin >10%, study personnel should:

Care for and medically stabilize the participant until there is no immediate risk of complications or death, if applicable. There is currently no known antidote for an overdose of enfortumab vedotin.

Notify the Medical Monitor as soon as they become aware of the overdose, to discuss details of the overdose (e.g., exact amount of enfortumab vedotin administered, participant weight) and AEs, if any.

Refer to [Section 10.3.7 Reporting Procedures for Special Situations] for reporting requirements for suspected overdose or other medication error.

6.8 Concomitant Therapy

Medications taken within 28 days prior to informed consent and up to the first dose of study medication will be documented on the appropriate case report form (CRF) as a prior medication.

Medications taken after the first dose of study medication up until the 30-day safety follow-up visit (EOT visit in [Table 1 Schedule of Assessments]) will be documented on the appropriate CRF as concomitant medication.

6.8.1 Allowed Concomitant Therapy

Concomitant chronic prednisone (or equivalent) may be used at a dose of ≤ 20 mg/day. Higher doses of prednisone (or equivalent) are permitted for limited duration to treat acute

conditions that arise during the study as medically indicated. The use of anti-emetics is permitted. Premedications for IRRs per Section [6.5.3](#) are permitted.

Therapies to manage enfortumab vedotin-associated toxicity as recommended in Section [6.5](#) are permitted, including growth factors, and transfusions.

Participants who are receiving strong CYP3A4 inhibitors or P-glycoprotein (P-gp) inhibitors concomitantly with enfortumab vedotin should be closely monitored for adverse reactions.

Routine prophylaxis with vaccines is permitted; it is recommended that vaccines used do not contain live micro-organisms. Antimicrobial prophylaxis or ongoing treatment of resolving and/or controlled infection is permitted during the study.

Participants with a positive hepatitis B surface antigen and/or anti-hepatitis B core antibody and a negative PCR assay at baseline should receive appropriate antiviral prophylaxis or regular surveillance monitoring as per local or institutional guidelines.

Participants with treated CNS metastases are permitted on study conditionally; participant with uncontrolled tumor-related bone pain or impending spinal cord compression requiring pain medication on a stable regimen is permitted as per Section [5.2](#).

Palliative radiotherapy on a non-target bone lesion that is not progressing is allowed after 3 cycles of treatment; must be administered after the initial response assessment and repeat scans described in Section [7.1](#). This will not be considered a subsequent anticancer therapy, but must not interfere with the assessment of tumor target lesions. Treatment with enfortumab vedotin should be interrupted during palliative radiotherapy.

6.8.2 Prohibited Concomitant Therapy

If the investigator determines that any of the following medications are necessary to provide adequate medical support to the participant, the participant must be withdrawn from further administration of the study treatment:

- a. Other investigational drugs and/or vaccines
- b. Chemotherapy or other medications intended for antitumor activity. This does not apply to participants on endocrine therapy, or to participants on agents intended for the treatment of bone metastasis where participants should be on a stable dose of bone targeting agents for at least 2 weeks prior to first dose of study drug (e.g., bisphosphonates, or receptor activator of nuclear factor kappa-B [RANK] ligand inhibitors).
- c. Radiation therapy except palliative radiation for non-target lesions (as described in Section [6.8.1](#)) that is approved by the sponsor. Note: Radiation therapy to a preexisting symptomatic solitary lesion or to the bone may be considered on an exceptional case-by-case basis after consultation with the sponsor.

7 STUDY PROCEDURES AND ASSESSMENTS

- Study procedures and their timing are summarized in the [[Table 1](#) Schedule of Assessments]. Adherence to the study design requirements, including those specified in the schedule of assessments, is essential and required for study conduct. Prospective protocol waivers or exemptions are not allowed.

- Any change, divergence or departure from the study design or procedures identified in the protocol is considered a protocol deviation. All deviations from the protocol are to be recorded.
- Immediate safety concerns should be discussed with the sponsor immediately upon occurrence or awareness to determine if the participant should continue or discontinue study treatment.
- All screening evaluations must be completed and reviewed to confirm that potential participants meet all eligibility criteria. The investigator will maintain a screening log to record details of all participants screened and to confirm eligibility or record reasons for screening failure, as applicable.
- Procedures conducted as part of the participant's routine clinical management (e.g., blood count) and obtained before signing of the ICF may be utilized for screening or baseline purposes provided the procedures met the protocol-specified criteria and were performed within the time frame defined in the schedule of assessments.

7.1 Efficacy Assessments

Measures of anticancer activity will be assessed by computed tomography (CT) scans with contrast approximately every 8 weeks (± 1 week). After 1 year on study, response assessments will be reduced to every 12 weeks (± 1 week). The schedule of response assessments should not be adjusted for dose delays/interruptions or other reasons for changes in the timing of a participant's study activities; timepoints for response assessments should be calculated from Cycle 1 Day 1. A CT scan with contrast (chest, abdomen, and pelvis) is the preferred modality for tumor assessment. Magnetic resonance imaging (MRI) is acceptable if CT scans are contraindicated in a participant (e.g., participant is allergic to contrast media). Participants must be evaluated using the same imaging method throughout the study for efficacy assessments. Other regions should be scanned if the participant has known or suspected disease in that region. Brain and/or bone scans should also be repeated at response assessment timepoints if bone metastases were identified at baseline, or if metastasis is known or suspected. Responses (CR or partial response [PR]) will be confirmed with repeat scans at least 4 weeks after first documentation of response. The schedule for response assessments should not be adjusted after the confirmatory scan (e.g., CR at Week 8, confirmatory scans at Week 12, next assessment due at Week 16). Tumor imaging should also be performed whenever disease progression is suspected. The determination of antitumor activity will be based on confirmed objective response assessments by IRC as defined by RECIST V 1.1. The investigator could make treatment decisions based on site assessments of scans by RECIST V 1.1.

Participants who discontinue study treatment for reasons other than objective disease progression by RECIST V 1.1 will continue to receive CT scans with contrast 8 weeks (± 1 week) after the previous response assessment scan and every 8 weeks (± 1 week) following the previous scan thereafter. After 1 year on study the frequency of response assessments will be reduced to every 12 weeks (± 1 week). The tumor assessments will continue until the participant has radiological disease progression per RECIST V 1.1 as determined by investigator, initiates a new anticancer therapy, dies, withdraws study consent, lost to follow-up or the study closes, whichever comes first. The determination of

antitumor activity will be based on confirmed objective response assessments as defined by RECIST V 1.1. Participants who do not have at least 2 (initial response and confirmation scan) post-baseline response assessments will be counted as non-responders. Clinical response of CR, PR, SD, or progressive disease (PD) will be determined at each assessment. Response and progression will also be assessed by IRC and investigator independently.

Survival status will be updated every 12 weeks (± 1 week) (calculated from disease progression) until death, study closure, lost to follow-up or withdrawal of consent from study, whichever occurs first.

Participants' clinical data must be available for CRF source verification. Tumor images will be submitted to a central imaging laboratory.

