1.2 Study Schema

Figure 1 Study Schema

Footnotes appear on next page

29 Mar 2022
Amendment 2

Astellas

Page 16 of 95

ADC: antibody-drug conjugate; EOT: End of Treatment; EV: Enfortumab vedotin; FU: follow-up; MMAE: monomethyl auristatin E; PK: pharmacokinetic; TAb: total antibody;

- a. Participants will have disease response assessments every 8 weeks (\pm 1 week) for the first year on study treatment. After 1 year from the start of treatment, the frequency of response assessments will be reduced to every 12 weeks (\pm 1 week). The schedule of response assessments should not be adjusted after the confirmatory scan.
- b. One to 2 study sites will be designated as the PK cohort site(s). Approximately 12 participants will be enrolled in PK cohort. Additional participants may be enrolled in PK cohort to compensate for participants who become unevaluable for the PK relevant primary endpoint (PK evaluable).
- c. Only participants that have not met radiographic disease progression in the Treatment Period will go into Post-Treatment Period, while participants that have met radiographic disease progression within the Treatment Period will go into the Long-Term Follow-Up directly.

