4 STUDY DESIGN AND DOSE RATIONALE

4.1 Overall Study Design

This is a single-arm, open-label, multi-center, Phase 2 study to assess the safety, efficacy and pharmacokinetics of enfortumab vedotin in Chinese participants with LA or mUC who have previously been treated with platinum-containing chemotherapy and PD-1/PD-L1 inhibitor therapy. Up to 40 participants will be enrolled including approximately 12 PK Chinese participants in the PK Cohort.

All participants will receive enfortumab vedotin at 1.25 mg/kg dose level administered as an IV infusion on Days 1, 8 and 15 of every 4-week (28 days) cycle. Participants will continue on study treatment until one or more of the following discontinuation criteria are met:

- Participant requests to stop treatment.
- Investigator decides it is in the participant's best interest to discontinue.
- Participant develops documented radiological disease progression per Response Evaluation Criteria in Solid Tumor (RECIST) V1.1 by investigator assessment.
- Participant starts a new anticancer therapy.
- Participant develops unacceptable toxicity.
- Female participant becomes pregnant.
- Participant is noncompliant with the protocol based on the investigator or medical monitor assessment.
- Participant did not receive study drug continuously for > 2 cycles (i.e., > 6 consecutive doses not received). Medical Monitor consultation is required after the participant was unable to receive one full cycle of study drug administration (i.e., 3 consecutive doses). Dose delays for patients who are responding to treatment may be extended beyond 8 weeks in consultation with Medical Monitor, if the patient's toxicity does not otherwise require permanent discontinuation.

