9.4.2.2.3 PFS per IRC

Progression-free survival (PFS) per IRC is defined as the time from start of study treatment to first documentation of objective tumor progression (PD per RECIST V 1.1) based on IRC assessment, or to death due to any cause, whichever comes first.

The median PFS and PFS at 6 and 12 months will be estimated using the Kaplan-Meier method and will be reported along with the corresponding 95% CI. Details on the definition of censoring will be provided in the SAP. This analysis will be conducted using the FAS.

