### **4.4 Secondary Endpoint(s) Analysis**

#### **4.4.1 Definition of Endpoint(s)**

The secondary endpoints are:

- Confirmed ORR per RECIST V1.1 per investigator assessment
- DOR per RECIST V1.1 per IRC and per investigator assessment

Duration of response (DOR) is defined as the time from first documentation of objective response (CR or PR that is subsequently confirmed) to the first documentation of PD or to death due to any cause, whichever comes first. DOR will only be calculated for the participants achieving a confirmed CR or PR.

DOOR will be censored as described below:

- If a participant has neither PD nor death, DOOR will be censored at the date of last evaluable radiological tumor assessment.
- If a participant starts a new anticancer treatment before any PD event or death, DOOR will be censored at the date of last evaluable radiological tumor assessment prior to the date of new anti-cancer treatment.

For a participant who is censored, the last evaluable radiological tumor assessment refers to the participant's last radiological tumor assessment where the response is CR PR or SD.

DOOR (in days) will be calculated as: (Date of documented disease progression or death or censoring) – (Date of the first CR/PR) +1.

To apply the cutoff date to DOOR is to exclude tumor assessments, death and anti-cancer therapy date after cutoff date in the analysis.

- DCR per RECIST V1.1 per IRC and per investigator assessment

Disease control rate (DCR) is defined as the proportion of participants with BOR of confirmed CR or confirmed PR or SD, per RECIST v1.1. Definition of BOR is specified in Section 4.3.1.

- PFS per RECIST V1.1 per IRC and per investigator assessment

Progression-free survival (PFS) is defined as the time from the date of first dose of study drug to the date of first documented radiological disease progression (PD) or death due to any cause, whichever comes first. PFS will be censored as the following:

- If a participant has neither PD nor death, PFS will be censored at the date of last evaluable radiological tumor assessment or at the first dose date if no evaluable postbaseline radiological assessment is available
- If a participant starts a new anticancer treatment before any PD event or death, PFS will be censored at the date of last evaluable radiological tumor assessment prior to the date of new anti-cancer treatment.

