### **4.4.3 Sensitivity Analysis**

The following sensitivity analysis will be performed for the DOR per IRC:

1. A sensitivity analysis to censor participants who progressed or died after an extended loss to follow up (i.e.,  $\geq 2$  consecutive missed response assessments) at the date of the last adequate response assessment prior to the missed visits.

The following sensitivity analysis will be performed for the PFS per IRC:

1. A sensitivity analysis to censor participants who progressed or died after an extended loss to follow up (i.e.,  $\geq 2$  consecutive missed response assessments) at the date of the last adequate response assessment prior to the missed visits.

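### Imaging stops at the investigator's PD call, so PFS and DOR per IRC are probably biased upward when the IRC has not yet called PD, and SAP 4.4.3 plans no analysis of this

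*Protocol*

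**What the plan says.** Treatment ends on the site's reading. One discontinuation criterion in Protocol 4.1 is: "Participant develops documented radiological disease progression per Response Evaluation Criteria in Solid Tumor (RECIST) V1.1 by investigator assessment". For participants already off treatment without progression, Protocol 7.1 continues scans until the participant "has radiological disease progression per RECIST V 1.1 as determined by investigator, initiates a new anticancer therapy", or until death, withdrawal, loss to follow-up or study closure. For those who progress on treatment, the footnote to the schema in Protocol 1.2 says that "participants that have met radiographic disease progression within the Treatment Period will go into the Long-Term Follow-Up directly"; in the Schedule of Assessments that period has survival contact but no CT. Nowhere is IRC agreement required before imaging ends.

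The two readings are separate. Protocol 7.1: "Response and progression will also be assessed by IRC and investigator independently". The event for PFS per IRC (Protocol 9.4.2.2.3) is "first documentation of objective tumor progression (PD per RECIST V 1.1) based on IRC assessment, or to death due to any cause, whichever comes first". SAP 4.4.1 gives two censoring rules: "If a participant has neither PD nor death, PFS will be censored at the date of last evaluable radiological tumor assessment" and "If a participant starts a new anticancer treatment before any PD event or death, PFS will be censored at the date of last" evaluable scan before that treatment. It defines an evaluable scan as one read as CR, PR or SD. DOR has matching rules.

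SAP 4.4.3 lists one sensitivity analysis for each of these endpoints: "A sensitivity analysis to censor participants who progressed or died after an extended loss to follow up", meaning at least two assessments missed in a row. The concordance summary in SAP 4.4.2.5 compares best overall response only. PFS and DOR per investigator are planned as secondary endpoints (SAP 4.4.2.6 and 4.4.2.8).

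**The concern.** Kaplan-Meier estimation assumes that a censored participant has the same outlook as those still under observation. A participant whose own investigator has just called progression plausibly does not. Censoring that participant at the same scan, because the IRC read it as SD or better, removes someone likely to have IRC PD soon, and the curve stays too high. If the participant dies before any new therapy, an event is counted, but at the date of death and not at the earlier date when further scans might have shown IRC PD.

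The study has no control arm to share such a bias. Protocol 2.1 describes it as a bridging study meant to show results consistent with the non-Chinese population, and Protocol 4.2 chose IRC review of response to limit bias. PFS and DOR per IRC describe how durable the effect is, so a reader should be able to see how far they depend on the stopping rule.

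**Working it through.** **Figures in the plan.** The documents give no event count, precision or discordance rate for PFS or DOR. Their only power figures are for ORR, and these reproduce: the smallest rejecting count with P(X ≥ r | 10%) ≤ 0.025 gives power at 35% of 87.6% (N=30, r=8), 95.8% (N=35, r=8), 97.0% (N=40, r=9) and 99.3% (N=50, r=10). Nothing below changes them.

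**Inputs.** Scans are every 8 weeks (Protocol 7.1). A median of 8 months is assumed; the Synopsis gives about 8 months as the anticipated time from first dose to progression but does not call it a median. The discordant share d = 10%, 20% or 30% and the lag between the investigator's and the IRC's call are also assumptions.

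**Reference value.** The chance of passing one 8-week interval without progression is q = 2^(−(56/30.4375)/8) = 0.8526. The last scan by 12 months is the sixth (day 336), so full IRC follow-up would show q^6 = 38.4%.

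**Effect of the censoring rule, lag of exactly one scan, deaths ignored.** At scan j ≥ 2 the fraction at risk is (1−d)q^(j−1) + d·q^j, and the fraction with an observed event is (1−d)q^(j−1)(1−q). The estimated hazard per scan is therefore

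h = (1−d)(1−q) / [(1−d) + d·q].

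The first scan keeps hazard 1−q, so the 12-month estimate is q(1−h)^5.

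| d | h | 12-month PFS, lag 1 scan | Simulated, lag 1–3 scans equally likely |
|---|---|---|---|
| 0 | 0.1474 | 38.4% | – |
| 10% | 0.1346 | 41.4% | 40.3% |
| 20% | 0.1215 | 44.6% | 42.5% |
| 30% | 0.1079 | 48.2% | 44.9% |

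Simulation of the one-scan case gave 41.3%, 44.6% and 48.1%, in line with the formula. When investigator calls were made unrelated to the IRC progression time, the same shares of censoring gave 38.3–38.4%, so no bias.

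**With deaths and new therapy.** A further simulation (lag of one scan, 12-week scans after one year) let half of the discordant participants start new therapy and assumed a median survival of 6 months after investigator PD. The reference varies slightly by run.

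| d | Full IRC follow-up | SAP 4.4.1 rule | SAP 4.4.3 analysis | Investigator PD as event |
|---|---|---|---|---|
| 10% | 38.3% | 40.8% | 40.7% | 37.6% |
| 20% | 38.9% | 43.8% | 43.7% | 37.3% |
| 30% | 38.4% | 46.4% | 46.3% | 35.9% |

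At d = 20%, if nobody starts new therapy, nobody is censored, yet the estimate is still 42.6% against 38.4% because the deaths come late. If all start new therapy, 16.9% are censored and the estimate is 44.9% against 38.8%.

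The SAP 4.4.3 analysis hardly moves the result because it adds censoring: at d = 20% the censored share rises from 8.5% to 13.3%. That run treats scans no longer scheduled after investigator PD as missed, which the SAP does not settle.

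**DOR.** This was not simulated. At an ORR of 35–44%, 40 participants give 14 to about 18 responders (0.35 × 40 = 14; 0.44 × 40 = 17.6). Discordance of 10–30% would then involve about 1 to 5 people.

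**The case against.** The strongest case on the other side has four parts.

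- A reader might infer that every early investigator call produces informative censoring. It does not. If the IRC reads PD on the same scan or an earlier one, nothing is lost, and a death before new therapy is an event. This stands and limits the point, although a death counted late still pushes the curve up.
- A reader might also infer that the bias must always lengthen the endpoints. The documents do not establish that. It depends on investigator calls foreshadowing IRC progression; with unrelated calls the bias was nil. An upward shift is the plausible direction, not a certainty, and a fixed one-scan lag is the upper end of the scenarios run.
- PFS and DOR per investigator are already planned, count investigator PD on its date and escape this mechanism. SAP 4.4.2.1 and 4.4.2.3 also tabulate new-therapy censoring. This stands in part. The investigator analyses change the reader for everyone, and DOR per investigator also changes the set of responders, so neither brackets the IRC estimate. No table shows how many were censored after investigator PD.
- Success rests on confirmed ORR alone, and PFS and DOR are descriptive. The approximate 95% half-width for 12-month PFS at N=40 is 1.96 × √(0.384 × 0.616/40) = 15 points, more than any bias shown here. This limits the priority. The confidence interval describes random error, however, and does not allow for a systematic shift.

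**Conclusion.** The gap is real but moderate. The stopping rule makes IRC PD unobservable once the investigator has called PD first, the SAP's censoring rule probably turns that into an upward bias in PFS and DOR per IRC, and no planned analysis examines it. Under the stated assumptions, 12-month PFS per IRC reads about 40–48% instead of about 38%, and the bias falls to zero if investigator calls carry no information about IRC progression. The median, discordance rate, lag, share starting new therapy and survival after PD are all assumptions. The size of any effect on DOR is unknown.

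Two stronger conclusions are not supported. The ORR test, its power and the success criterion are untouched. Nor can it be said that comparison with EV-201 would be distorted, because the documents do not say how that study stopped scans or censored.

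**What to change.** In SAP 4.4.3 add, for PFS per IRC and for DOR per IRC, a supplementary analysis in which the event is the earliest of IRC PD, investigator PD without IRC PD, start of new anticancer therapy, or death, each on its own date. Present it as a lower bracket beside the main estimate, not as a replacement. Partial therapy start dates can follow the existing rule in SAP 4.11.2.

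In the tables of SAP 4.4.2.1 and 4.4.2.3, report separately the participants censored after investigator PD without IRC PD.

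The cost is two extra Kaplan-Meier analyses and one table row from data already collected. The supplementary estimates will be somewhat shorter than the main ones. No extra scans are needed and the main analyses stay as planned.
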